## 6.5 Summary of the literature

1. The majority of studies investigating OSA in women with PCOS were conducted in the USA. The prevalence of OSA in women with PCOS in the reported studies ranged from 0 – 69% (Median 55.8%, Mean 39.8%). The reason for this wide range in OSA prevalence is probably a combination of using different cut-offs and different methods to diagnose OSA; small studies sample size; and selection bias.
2. The data available suggest that the risk for OSA in women with PCOS is, as expected, increased with age and obesity. However, while it is probable that PCOS precedes the development of OSA, it is also possible that OSA precedes and increases the risk of developing PCOS in some women. Observational long-term studies are needed to assess how frequent is the development of OSA in women with PCOS and vice versa.
3. It seems plausible that OSA is a marker of severity in PCOS; however, it is difficult to conclude that from the studies conducted so far as abdominal adiposity and ethnicity have often not been accounted for in these studies. In addition, the relationship between OSA and hyperandrogenism in PCOS seems controversial. It is also not known if the presence of OSA in women with PCOS is associated with worse clinical outcomes including oligomenorrhoea, hirsutism, subfertility, depression, impaired quality of life, type 2 diabetes or cardiovascular disease. Subsequently, well conducted observational studies are needed to examine the effects of OSA in women with PCOS.
4. While one study suggested that CPAP therapy in women with PCOS and OSA improves insulin sensitivity and reduces blood pressure, it is not clear if this will translate into long-term meaningful clinical outcomes. Interventional, randomised-controlled trials with long-term follow up are needed to assess the effect of CPAP therapy on clinical and metabolic function in women with PCOS and OSA.

## 6.6 Justification for the study

PCOS and OSA are common conditions that are associated with obesity. PCOS is associated with subfertility, depression and anxiety, impaired QoL, increased risk of type 2 diabetes, and high prevalence of OSA. Hyperandrogenism and low progesterone levels are commonly seen in women with PCOS and may explain the increased prevalence of OSA. OSA is associated with disturbed sleep pattern, increased IR, disturbed hypothalamic/pituitary/ovarian axis, and sympathetic overactivity and subsequently may lead to a more severe phenotype of PCOS in affected women. Data from studies investigating the relationship between OSA and PCOS are limited by small sample size; not accounting for important confounders; and being at risk of selection bias. In addition, the effects of OSA on clinical outcomes in women with PCOS have not been investigated. Subsequently well conducted large observational studies are needed to investigate the relationship between OSA and clinical outcomes in women with PCOS. This is particularly important as OSA is a treatable condition.

## 7. Hypothesis

Women with PCOS and OSA, compared to women with PCOS only, have more severe clinical and biochemical features of PCOS and impaired QoL.

## 8. Study aims

Primary outcome:

- To examine if OSA is associated with impaired QoL in women with PCOS.

Secondary outcomes:

- To assess the relationship between OSA and body composition, hirsutism (modified Ferriman-Gallwey score), period cyclicality, reproductive outcomes, insulin resistance (HOMA-IR), hyperandrogenism, depression and anxiety, FPG, glycated haemoglobin (HbA1C), reproductive hormone profile, lipids, and inflammation (high sensitivity C-reactive protein, hCRP) in women with PCOS.

## 9. Study design

Observational cross-sectional study

## 10. Study groups

### 10.1 Source of subjects

Women with PCOS will be recruited consecutively from the PCOS clinic at the WISDEM centre, University Hospital Coventry. In addition, patient information sheet (PIS) and a study invitation letter will be sent to women with PCOS who attended the PCOS clinic in the last 12 months.

### 10.2 Inclusion criteria

- Women with PCOS, defined by the Rotterdam criteria as 2 out of 3:
  1. Oligo/anovulation
  2. Clinical or biochemical evidence of hirsutism
  3. Polycystic ovaries on ultrasound.

And the exclusion of other disorders with similar presentation including NC-CAH, androgen secreting tumours, Cushing's syndrome; thyroid disorders and prolactinomas.

- Age  $\geq$  18 years.
- Able to provide written consent.
- Able to adequately understand English.
- Patients with unknown diagnosis of OSA, or who were investigated in the past and either found not to have OSA, or found to have OSA and are not on CPAP therapy.

### 10.3 Exclusion criteria

- Pregnancy or breastfeeding women.
- Patients who are unable to give consent.
- Patients known to have OSA treated with CPAP.

- Anyone under the age of 18 years.
- Unable to adequately understand or speak English.

#### **10.4 Expected number of eligible subjects**

In the PCOS clinic we usually see around 8 - 10 women with suspected PCOS per week. We expect 5 – 6 of them will fulfil the inclusion and exclusion criteria and of those we expect 3 – 4 to agree to take part in the study.

#### **11. Recruitment and choosing participants**

##### **– Method of recruitment**

Patients will be given the PIS by the study investigator or clinic nurse while sitting in the waiting area before being seen in the PCOS clinic. They will be advised to take the PIS home and call back if they are happy to take part in the study or if they have any question related to the study. In addition, an invitation letter and study PIS will be sent to patients who attended the PCOS clinic in the last 12 months. A list of patients who attended the PCOS clinic within the last year will be generated and from this list we will identify patients with confirmed diagnosis of PCOS and we will send the PIS and invitation letter to them by post.

Patients will also be recruited from the Weight Management Clinic and the reproductive endocrinology clinic where the PIS will be given to patients with a history of PCOS by the clinic doctor. Patients will be advised to take the PIS home and call back if they are happy to take part in the study or if they have any questions related to the study.

A poster inviting women with a history of PCOS to take part in the study will be displayed at University Hospital Coventry and an e-poster will be displayed at the hospital intranet. Women who answer the advert will be sent the PIS and advised to call back if they would like to take part or if they have any question about the study.

##### **– Procedures to assess study suitability**

Initial biochemical and clinical screening to confirm the diagnosis of PCOS and investigate the likelihood of OSA will be performed as part of routine clinical care in the National Health Service (NHS).

For patients who self-refer through the advertisement, the study doctor will clarify the diagnosis of PCOS with them on the phone and if the diagnosis is not clear, they will be offered the chance to be seen in the PCOS clinic if they wish.

##### **- Consent**

We expect patients to have the PIS for at least 24 hours before making a decision about taking part in the study. Patients who agree to take part in the study and have a confirmed diagnosis of PCOS will be invited for a study visit. Consent will be obtained by a study doctor/investigator from all study participants before taking part in any study related activity.

## - Participants

38 women will be recruited after fulfilling the inclusion and exclusion criteria. Study participants will be screened for OSA using Berlin and Epworth Sleepiness Scale (ESS) questionnaires and if both were normal then no further testing for OSA is required. If the score on either of the questionnaires was abnormal then home-based sleep studies will be arranged and the patient will be referred to the Respiratory Physician as per routine clinical care.

OSA will be assessed by a single overnight home-based cardiorespiratory sleep study using a portable multichannel device (Alice PDx, Philips, US) and scored in accordance with the International Classification of Sleep Disorders (ICSD-3) (American Academy of Sleep Medicine 2014). The scoring of the sleep studies will be performed by [name], Respiratory Physician, or a sleep technician. Sleep studies with <4 hours of adequate recordings will be repeated and excluded if the quality remained poor. OSA is defined by either an AHI of  $\geq 5$  with daytime sleepiness as well as gasping, choking or snoring; or an AHI of  $\geq 15$  in the absence of symptoms (American Academy of Sleep Medicine 2014).

Participants will be divided into two groups depending on the results of the ESS and Berlin questionnaires and sleep studies:

1. PCOS low risk OSA: women with PCOS with either normal scores on both the ESS and Berlin questionnaires, or who had normal sleep studies.
2. PCOS OSA: women with PCOS who had sleep studies confirming the presence of OSA.

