In another study (Chatterjee et al. 2014), 50 women with PCOS (BMI 27.1 kg/m^2) were screened for OSA and 33 (66%) were found to have sleep disordered breathing (SDB). Women with PCOS were randomly selected from the gynaecology and reproductive endocrinology clinics. PCOS was diagnosed based on the Rotterdam criteria. SDB was defined as an RDI of ≥5 events/hour along with symptoms or an RDI of >15 events/hour with or without associated symptoms. Differences between women with PCOS and OSA to women with PCOS without OSA are summarised in Table 1. On logistic regression analysis which adjusted for BMI, only the associations between fasting plasma glucose and diastolic blood pressure with SDB remained significant. Study limitations include that the age of study participants was not provided and small study sample.

Finally, in an interventional study (Tasali et al. 2011) 19 obese women with PCOS and OSA [age (±SEM) 31.2 ±1.2 year, BMI 46.4 ±2.4 kg/m^2] were treated with CPAP for 8 weeks with subsequent improvement in insulin sensitivity (relative increase of nearly 7%), and reduction in diastolic blood pressure (around 2.3mmHg). Day-time and night-time norepinephrine levels also reduced after therapy. Study limitations include that the authors only performed 'per protocol' analysis including only 9 women, and data from 10 participants were excluded from the analysis as their average use of CPAP was less than 4 hours per night. In addition, the study did not include a control group. It is also not clear if the changes in insulin sensitivity and blood pressure observed in the study will translate into meaningful clinical outcomes.

Study	Notes	n	OSA		Women with PCOS and OSA compared to women with PCOS without OSA										
			Diagnosis	%	Weight or BMI	Waist or WHR	IR	Hyperandrogenism	BP	FPG	IGT	MS	FSH / LH	Clinical features	QoL/ Depression
(Vgontzas et al. 2001)	USA	53	AHI ≥10 + symptoms	11–17%	↑	NA	Insulin ↑*	Free and TT ↔	NA	↔	NA	NA	NA	NA	NA
(Fogel et al. 2001)	USA	18	AHI >10	66.8%	NA	↑	NA	NA	NA	NA	NA	NA	NA	NA	NA
(Gopal et al. 2002)	USA	23	RDI ≥5 + symptoms	69.6%	↔	NA	NA	NA	NA	NA	NA	NA	NA	NA	NA
(Tasali et al. 2008)	USA	52	AHI ≥5	55.8%	↑	NA	HOMA-IR ↑*	Free and TT ↔	NA	↔	↑	NA	NA	NA	NA
(Yang et al. 2009)	Taiwan, slim women	18	AHI ≥ 5	0%											
(de Sousa et al. 2010)	Germany, adolescents	22	Not stated	0%											

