### 13.5 Clinical history

**Period cyclicity:** Women will be asked to estimate how many periods they had in the four months preceding the study visit. We accept that there is a risk of recollection bias with this method. For participants using hormonal contraception, this information will not be collected.

**Hirsutism:** This will be assessed using the modified Ferriman-Gallwey score (Appendix). The modified Ferriman-Gallwey scoring system (Ferriman and Gallwey 1961) is a useful clinical tool, though subjective, in assessing hirsutism. Women are asked to assess the degree of their body hair using pictures of nine body areas and to give a score ranging from 0 (absence of terminal hair growth) to 4 (heavy terminal hair growth) for each area. A total score of 8 or more on the modified Ferriman-Gallwey scoring system is widely considered suggestive of hirsutism (DeUgarte et al. 2006).

**Risk of OSA:** The risk of OSA will be assessed as per clinical practice using the Berlin and ESS questionnaires. Although the ESS (Appendix) is commonly used, it mainly assesses sleepiness (Johns 1991). A score of more than 10 on the ESS is consistent with excessive daytime sleepiness. The Berlin questionnaire (Appendix) assesses the risk of OSA and has a sensitivity of around 85% (Netzer et al. 1999).

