### 3. Berlin Questionnaire

#### Berlin Questionnaire® Sleep Apnea

Height (m) \_\_\_\_\_ Weight (kg) \_\_\_\_\_ Age \_\_\_\_\_ Male / Female

Please choose the correct response to each question.

##### Category 1

1. Do you snore?

- a. Yes
- b. No
- c. Don't know

*If you answered 'yes':*

2. Your snoring is:

- a. Slightly louder than breathing
- b. As loud as talking
- c. Louder than talking
- d. Very loud. Could be heard in adjacent rooms.

3. How often do you snore?

- a. Almost every day
- b. 3-4 times per week
- c. 1-2 times per week
- d. 1-2 times per month
- e. Rarely or never

4. Has your snoring ever bothered other people?

- a. Yes
- b. No
- c. Don't know

5. Has anyone noticed that you stop breathing during your sleep?

- a. Almost every day
- b. 3-4 times per week
- c. 1-2 times per week
- d. 1-2 times per month
- e. Rarely or never

##### Category 2

6. How often do you feel tired or fatigued after your sleep?

- a. Almost every day
- b. 3-4 times per week
- c. 1-2 times per week
- d. 1-2 times per month
- e. Rarely or never

7. During your waking time, do you feel tired, fatigued or not up to par?

- a. Almost every day
- b. 3-4 times per week
- c. 1-2 times per week
- d. 1-2 times per month
- e. Rarely or never

8. Have you ever nodded off or fallen asleep while driving a vehicle?

- a. Yes
- b. No

*If you answered 'yes':*

9. How often does this occur?

- a. Almost every day
- b. 3-4 times per week
- c. 1-2 times per week
- d. 1-2 times per month
- e. Rarely or never

##### Category 3

10. Do you have high blood pressure?

- Yes
- No
- Don't know

The test is suggestive of OSA if two or more categories were positive. Category 1 is positive if 2 or more responses were positive (shaded areas). Category 2 is positive if 2 or more responses were positive. Category 3 is positive if the patient had a history of hypertension or BMI>30kg/m^2 (Netzer et al. 1999).

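### The AHI ≥15 route to OSA requires absent symptoms, but every woman given a sleep study has a symptom-type positive screen, so some women with AHI ≥15 have no defined group

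*Combined protocol and SAP*

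**What the plan says.** Section 11 (Participants) sets the gate to testing. On the Berlin and ESS questionnaires, "if both were normal then no further testing for OSA is required". Otherwise, "If the score on either of the questionnaires was abnormal then home-based sleep studies will be arranged".

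The same section gives two alternative limbs for OSA. The first is an AHI of at least 5 "with daytime sleepiness as well as gasping, choking or snoring; or an AHI of" at least 15, where the second limb begins, and that limb applies "in the absence of symptoms (American Academy of Sleep Medicine 2014". The section does not say which symptoms must be absent.

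The low-risk group takes women with both questionnaires normal, or with a normal sleep study. No group is named for a study that is neither normal nor OSA.

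Three other places bear on this:
- Section 13.5, on the ESS: "A score of more than 10 on the ESS is consistent with excessive daytime sleepiness".
- Appendix 3, on the Berlin questionnaire: "The test is suggestive of OSA if two or more categories were positive". Category 1 covers snoring and witnessed pauses, and Category 2 covers tiredness and nodding off at the wheel. Category 3 is the only one not based on symptoms: "Category 3 is positive if the patient had a history of hypertension or BMI>30kg/m".
- Section 6.2 lists snoring, sleepiness and fatigue, among others, as symptoms of OSA.

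**The concern.** The second limb asks for something the entry gate largely rules out. A woman reaches the sleep study because she has reported a symptom, and is then required to have none. Women with a high AHI and an incomplete symptom set fall between the two limbs.

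OSA status is the predictor of interest in the primary models in section 14.2 and defines both study groups. If the rule is applied as written, nearly every OSA case must be sleepy. The Summary (section 5) names excessive daytime sleepiness as one way in which OSA may impair quality of life. Exposure would then be partly selected on a feature close to the outcome, instead of on sleep-disordered breathing. Cases could also be lost from a group planned at only 15.

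**Working it through.** **1. Does every route into testing carry a symptom-type positive?** Take Berlin Categories 1, 2 and 3 and ESS >10 as yes or no, which gives 16 patterns.
- ESS >10: 8 patterns, all tested. ESS >10 is itself sleepiness.
- ESS ≤10 with at least two Berlin categories positive: 4 patterns (1+2, 1+3, 2+3, 1+2+3). Category 3 alone is not enough, so each includes Category 1 or 2.

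That makes 12 tested patterns, and none of the 12 is free of a symptom-type positive.

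**2. Who meets which limb at AHI ≥15?** Split Category 2 into fatigue and drowsy driving, because fatigue is not named in the section 11 sentence. Treat Category 1 positive as snoring, and ESS >10 or drowsy driving as sleepiness. Treat a negative Category 1 as no snoring. This gives 26 screen-positive profiles.

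| Reading of the second limb | Meet limb 1 | Meet limb 2 only | Meet neither |
|---|---|---|---|
| None of the OSA symptoms in section 6.2, including fatigue | 12 | 0 | 14 |
| None of the symptoms named in the section 11 sentence | 12 | 1 | 13 |
| Anyone lacking the full limb 1 set | 12 | 14 | 0 |

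The single profile in the second row is fatigue plus Category 3, with no snoring and ESS ≤10. These are counts of possible profiles, not proportions of patients.

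**3. Three constructed records, applying the rule as written (first two readings).**

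| Record | Why tested | Limb 1 | Limb 2 | Group |
|---|---|---|---|---|
| AHI 40, loud nightly snoring, BMI 36, ESS 6, not sleepy | Berlin 1+3 | Fails: not sleepy | Fails: snores | None |
| AHI 22, ESS 14, no known snoring, gasping or choking | ESS | Fails: no nocturnal symptom | Fails: sleepy | None |
| AHI 6, ESS 12, snores | ESS | Meets | n/a | PCOS OSA |

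The mildest record is classed as OSA. The two more severe ones are not, and neither study can readily be called normal.

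**4. Effect on power.** First, the plan's own figure. Table 3 in section 14.1 gives SDs of 18.72 and 17.67, so the pooled SD is √[(18.72² + 17.67²)/2] = 18.2. The difference is 75.41 − 57.65 = 17.76, and 17.8/18.2 = 0.98. For a two-sided 5% t-test, the noncentrality is d × √[n₁n₂/(n₁+n₂)]. With 15 and 23 it is 0.98 × √(345/38) = 2.95 on 36 degrees of freedom, and power is 81.9%. This agrees with the plan's claim of 80%.

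The number of women lost is an assumption, because the documents give no AHI or symptom frequencies. With 23 low-risk women kept and no replacement:

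| Cases lost | Groups | Noncentrality | Power |
|---|---|---|---|
| 0 | 15 v 23 | 2.95 | 81.9% |
| 1 | 14 v 23 | 2.89 | 80.3% |
| 2 | 13 v 23 | 2.82 | 78.3% |
| 4 | 11 v 23 | 2.67 | 73.6% |

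**The case against.** The strongest reply is that the intent is clear. The second limb can be read as covering any woman with AHI ≥15 who lacks the first limb's symptom set. On that reading all 26 profiles are OSA and there is no gap, and a respiratory physician would hardly class AHI 40 as anything else. This is probably what was meant, but the sentence does not say it. Scoring may be done by a physician or a technician, and the sentence is the plan's only operational definition. Section 6.4 describes one published definition as "or an RDI of >15 events/hour with or without associated symptoms". That shows clearer wording was available. It does not prove intent here, since it reports another study's rule, based on RDI.

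Three stronger claims are tempting, and the documents do not support them:
- **That nobody can meet the second limb.** This holds only if fatigue counts as a symptom. Section 6.2 supports that, but section 11 leaves the term undefined. On the symptoms named in its own sentence, a fatigued woman with BMI >30, no snoring and ESS ≤10 qualifies. Such women are plausible, because section 11 also recruits from the Weight Management Clinic.
- **That the low-risk group is contaminated.** A tested woman enters that group only with a normal sleep study, and AHI 22 or 40 is hard to describe so. As written, these women have no group, so a power loss computed by moving them into the comparator is not warranted.
- **That a particular number of women is affected.** Any such number rests on assumed symptom frequencies. The gate selects on snoring and sleepiness together, so general frequencies would be doubtful among tested women.

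It is also fair to say that the same sentence leaves women with AHI 5 to 14.9 and an incomplete symptom set unassigned. That gap is related but separate: there a symptom condition was intended.

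**Conclusion.** The point holds in limited form. The second limb conflicts with the screening gate. Followed as written, the rule leaves women with AHI ≥15 and a partial symptom set outside both groups: 13 or 14 of the 26 screen-positive profiles, depending on whether fatigue counts. Of the profiles that can be classed as OSA, all are sleepy, except for one under the narrower reading. Exposure is therefore tied largely to sleepiness.

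The gate logic in step 1 follows from the documents alone. The profile counts also rest on equating Category 1 with snoring, and ESS >10 or drowsy driving with sleepiness. The power figures are illustrations for an unadjusted comparison of one domain at the planned effect size. They show that losing two cases takes power just below 80%, not that two will be lost. The rule should be settled before groups are assigned, so that membership does not depend on who reads the sentence or when.

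**What to change.** For the research grouping in section 11, reword the second limb to: *or an AHI of ≥15, with or without symptoms*. State that every woman with a valid study and AHI ≥15 is assigned to PCOS OSA. This removes the ambiguity under all three readings.

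The cost is one phrase and one sentence in the protocol, with no extra data, visits or participants. Clinical care is untouched, because sections 11 and 15 already refer women with an abnormal screen whatever their study group. The change does not settle the AHI 5 to 14.9 women, who need their own stated assignment.

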### 14.2 Statistical analysis

Continuous baseline characteristics for each of the PCOS OSA and PCOS low risk OSA groups will be summarised using the mean ( $\pm$ SD) and the median (interquartile range). If the data are approximately normally distributed, the means for the two groups will be compared using the independent t-test. If the data are not normally distributed, the two groups will be compared using the Mann-Whitney U test. Data will be checked for normality using the Shapiro-Wilk test (Razali and Wah 2011). Categorical baseline characteristics for each of the PCOS OSA and PCOS low risk OSA groups will be summarised by reporting the count and percentages in each category. The two groups will be compared using the chi-squared test.

To compare quality of life for the PCOS OSA and PCOS low risk OSA groups, we will fit linear models for each of the primary outcomes of interest (domain scores on the PCOSQ and WHOQOL-BREF questionnaires). The dependent variable in a linear model will be a primary outcome and independent (predictor) variable of interest will be whether a woman is from the PCOS OSA or PCOS low risk OSA group. As the groups may be imbalanced in other predictors for the primary outcomes, the models will adjust for potential confounders such as age, BMI, WHR, use of oral contraceptive pill, ethnicity, education level, marital status, other ongoing illnesses, and parity. Data will be assessed if they are approximately normally distributed; and if they are not, they will be transformed, for example, by taking the logarithm of the outcome variables.

Correlations will be evaluated using Pearson's coefficient (or Spearman's coefficient for non-normally distributed data). A two tailed P value of <0.05 will be considered statistically significant. Statistical analysis will performed using the SPSS statistics package (SPSS Inc., Chicago, USA).

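### The low-risk comparator pools untested screen-negative women with study-normal women, so the OSA contrast can show a QoL deficit even if OSA has no effect

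*Combined protocol and SAP*

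**What the plan says.** Section 11 (Participants) screens all women with the ESS and the Berlin questionnaire. For women normal on both instruments, the rule is: "if both were normal then no further testing for OSA is required". For the rest: "If the score on either of the questionnaires was abnormal then home-based sleep studies will be arranged".

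The triggers are as follows.
- **ESS.** Section 13.5: "A score of more than 10 on the ESS is consistent with excessive daytime sleepiness". This is enough by itself.
- **Berlin.** Appendix 3 requires two of three categories: snoring or witnessed apnoea; tiredness, with items such as "During your waking time, do you feel tired, fatigued or not up to par"; and a third, where "Category 3 is positive if the patient had a history of hypertension or BMI" is above 30 kg/m². Section 13.5 adds: "The Berlin questionnaire (Appendix) assesses the risk of OSA and has a sensitivity of around 85" per cent.

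The PCOS OSA group consists of women whose study confirmed OSA. The comparator is "women with PCOS with either normal scores on both the ESS and Berlin questionnaires, or who had normal sleep studies". Section 11 defines OSA as AHI of at least 5 with daytime sleepiness and snoring, choking or gasping, or AHI of at least 15 without symptoms.

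The primary outcomes in section 14.2 are PCOSQ and WHOQOL-BREF domain scores. The exposure is a single binary term: "predictor) variable of interest will be whether a woman is from the PCOS OSA or PCOS low risk OSA group". The covariate list includes age, BMI and WHR. It names neither screening status nor tiredness, and no analysis is limited to women who had a sleep study or uses AHI itself.

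**The concern.** Being tested, and so being able to enter the OSA group, depends partly on self-reported sleepiness and tiredness. Both can arise from many causes, and both go with poorer self-reported QoL; the Summary (section 5) itself names daytime sleepiness and reduced mood as routes to impaired QoL. The comparator includes women who passed the screen and were never tested. The planned contrast therefore partly compares screen-positive with screen-negative women, whatever their AHI.

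At stake is the primary aim, whether OSA is associated with impaired QoL. The secondary body-composition comparison is exposed too, because BMI above 30 is one way to score a Berlin category. Section 6.4 lists symptom-driven polysomnography as a limitation of a retrospective study in adolescents, so the authors recognise this kind of selection.

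**Working it through.** **1. The plan's own figure.** From Table 3, 75.41 − 57.65 = 17.76. The pooled SD is √[(18.72² + 17.67²)/2] = 18.2, so d = 17.76/18.2 = 0.98. Exact two-sided 5% t-test power at d = 0.98 is 0.795 for 14 + 22, 0.812 for 15 + 22 and 0.820 for 15 + 23. The stated 38 reproduces closely. The standard error of the unadjusted difference is 18.2 × √(1/15 + 1/23) = 6.0 points.

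**2. Who can be in each group.**

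| Screen | Sleep study | Group |
|---|---|---|
| ESS and Berlin both normal | none | low risk |
| either abnormal | normal | low risk |
| either abnormal | OSA confirmed | OSA |

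A tested woman with AHI 5–14 and no symptoms is not clearly placed: she does not meet the OSA definition, and her study is not plainly normal.

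**3. Expected gap if OSA has no effect.** Let u be the screen-negative share of the comparator. Let D be the QoL deficit of screen-positive relative to screen-negative women, whatever their AHI. With screen-negative mean m, the OSA group has mean m − D and the comparator m − (1 − u)D. The difference is −u × D. The documents give neither u nor D, so both are assumed below (15 vs 23, SD 18.2, t-test, 40,000 simulated trials per cell). Each cell shows the spurious gap in points and the two-sided rejection rate.

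| D | u = 6/23 | u = 12/23 | u = 17/23 | u = 1 |
|---|---|---|---|---|
| 5 | 1.3; 5% | 2.6; 7% | 3.7; 9% | 5.0; 13% |
| 10 | 2.6; 6% | 5.2; 12% | 7.4; 21% | 10.0; 37% |
| 17.8 | 4.6; 10% | 9.3; 28% | 13.2; 52% | 17.8; 82% |

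At u = 0 the rate is 5%. The last row uses the whole Table 3 difference and is an upper case. Where the model adjusts for BMI, D means what is left after that adjustment.

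**4. Does BMI adjustment remove it?** An illustrative population of 2,000,000 women was put through the ESS, Berlin and AHI rules. AHI had no effect on QoL, and tiredness was independent of AHI given BMI. Assumed: BMI mean 33, SD 7; tiredness costs 5 or 9 points per SD; BMI costs 0 or 3 points per SD. This gave 61% screen-positive, 22% in the OSA group (the plan assumes 40%) and u of about 0.5.

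| Contrast, no true effect | Gap (points) |
|---|---|
| Planned grouping, unadjusted | −2.48 to −7.15 |
| Planned grouping, BMI-adjusted | −1.84 to −3.32 |
| All women tested, symptom-based definition, BMI-adjusted | −1.14 to −2.05 |
| All women tested, AHI alone (≥5 or ≥15), BMI-adjusted | about 0.0 |
| Screen-positive only, OSA vs no OSA, BMI-adjusted | −0.42 to −0.76 |

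Adjustment removes much of the obesity route but not the sleepiness route. The third row shows a second source: at AHI 5–14 the case definition itself requires sleepiness, so the binary exposure stays symptom-selected even among tested women.

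The sign of the residual in tested women depends on the model. Other null simulations gave −1.3 to +0.9 for the sleep-studied contrast, and +1.0 to +1.8 for OSA versus AHI below 5.

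**5. Missed OSA among the untested.** With sensitivity 0.85 (section 13.5), prevalence p = 0.398 (the mean in section 6.5) and assumed specificity s, the undetected share among Berlin-negative women is 0.15p/[0.15p + (1 − p)s]. For s = 0.8 this is 0.0597/(0.0597 + 0.4816) = 11%; for s = 0.5 it is 0.0597/(0.0597 + 0.301) = 17%. Untested women are also ESS-normal, so this tends to overstate the misses. If OSA lowers QoL, these women pull the comparator down and shrink the contrast.

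**The case against.** The best defence is that the bias is modest. A gap of 2 to 5 points is about 0.3 to 0.8 of a standard error (2/6.0 to 5/6.0), and the study is sized for 17.8. BMI and WHR are already in the model, the covariate list is open-ended, and every quantity except the SD is assumed. All of that stands, and it bears on severity. It does not answer the structural point, since nothing in section 14.2 separates OSA from screening status.

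Three stronger readings are tempting, and the documents do not support them.
- A reader might infer that the untested women are free of fatigue and obesity. They need not be. Tiredness alone, or BMI above 30 alone, leaves the Berlin negative; and a hypertensive snorer is tested whatever her weight. Only an ESS above 10 is sufficient alone.
- A reader might infer that exposure is defined by the primary outcome. The ESS and Berlin are not outcomes. They are correlates of QoL, and sleepiness may also be a route by which OSA acts. For the same reason, adding ESS as a covariate is not a clean remedy.
- A reader might infer that the pooled and sleep-studied analyses bracket the truth. The sign of the residual bias in the subset varies with the model, so only the claim that it lies nearer zero is supported.

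**Conclusion.** The concern holds. The planned contrast can show a QoL deficit in the OSA group when OSA has no effect, because all of that group and only part of the comparator is screen-positive, and the planned adjustment does not cover this. A half screen-negative comparator with D of 5 to 10 gives 2.6 to 5.2 points; the BMI-adjusted model gives 1.8 to 3.3. Roughly 2 to 5 points is a fair summary, but it is illustrative: u, D and the model inputs are assumptions.

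A reader might conclude that the design is biased toward its hypothesis in every case. That holds under no OSA effect. If OSA has a real effect, missed cases dilute it, and the documents do not show which force is larger. The mechanism is certain and the size is not. This should be corrected in the analysis plan, but it does not invalidate the study.

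**What to change.** Keep the screening pathway and the pooled comparison. Add the following to section 14.2, before the data are examined.

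1. Companion analyses of the primary QoL models, and of body composition, limited to women with an adequate sleep study. The main companion uses AHI as a continuous predictor, which avoids the symptom requirement at AHI 5–14 and keeps women with AHI 5–14 and no symptoms. The second compares OSA with no OSA.
2. QoL summaries for never-studied and study-normal women separately, as well as pooled.
3. A rule for the conclusion: judge attribution to OSA by the estimate and 95% CI in the sleep-studied analysis. Unless these support an association, describe the result as screen-positive, study-confirmed OSA versus all others, and not as an effect of OSA itself.

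Agreement in sign between the two analyses should not be the test. They share all the OSA cases, so it is nearly automatic. In a null simulation with 15 OSA women against 12 studied and 11 unstudied comparators (an assumed split) and D of 5, 9.3 or 17.8, the sleep-studied difference had the same sign in 99.9%, 99.9% and 98.8% of falsely significant pooled results in the hypothesised direction.

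The cost is plan wording and a few models on data already collected. The downside is that the sleep-studied subset is smaller and less precise, with some residual selection that is probably small and of uncertain sign. It therefore accompanies the pooled analysis and does not replace it.
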